3.3.3 Caregiver recruitment

Patients may refer their caregivers (e.g., spouse, partner, children, friend) to contact the study team if interested, or if they prefer to share the caregiver's phone number, the study team contact them by phone and invite them. With the patients' consent, patients' caregivers are also invited to participate by phone, or mail. They will participate in a brief REDCap survey to report any changes related to confusion or delirium in the patient once *before* surgery, and once per week for 4 weeks *after* surgery (FAM-CAM attached). Additionally, some patients' caregivers (up to 25) will be invited to participate in a semi-structured interview (see Appendix J) after the patient's participation in the intervention has been completed.

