4.3.3 Exploratory Feasibility Outcomes

Implementation potential

Completeness of planned RCT primary outcome data collection at specified timepoints

Table 2. Feasibility study outcomes and potential study primary and secondary outcomes for planned RCT. Note: The surveys and questionnaires will be administered via email or research coordinators over the telephone.

Outcomes	Specific measure: description	Source	Timepoint
Reach (Primary)	Reach of the study: patients who agreed to participate in the study out of total eligible to participate Reach of the intervention bundle: patients who completed the interventions out of patients who agreed to participate in the pilot	Electronic Health Record, Research data warehouse	End of Study
Completeness of planned RCT primary outcome data collection at specified timepoints (Secondary)	Defined as a percentage of instrument or data fields completed for- Patient Health Questionnaire Anxiety and Depression Scale (PHQ-ADS) ⁶² : 16-item scale with components of the Patient Health Questionnaire-9 and Generalized Anxiety Disorder Scale (collected at baseline; 1 mo; 3 mo)	Research data warehouse	End of Study
Implementation-Potential (Exploratory)	Acceptability, appropriateness and feasibility of the interventions: The Acceptability of Intervention Measure (AIM), the Intervention Appropriateness Measure (IAM), and the Feasibility of Intervention Measure (FIM). ⁷⁷ Each survey has 4 items in a Likert scale ranging from completely disagree to completely agree.	Surveys	End of Study

Completeness of planned RCT secondary outcomes data collection at specified timepoints (Exploratory)	
We will be measuring the completeness of data collection for the following potential secondary outcomes for the planned RCT secondary outcomes:
 
 • Quality of Life (collected at baseline; 1 mo; 3 mo) • In-hospital delirium incidence (collected at baseline; in-hospital/postoperatively) • Post-discharge falls (collected at baseline; 1 mo; 2 mo; 3 mo) • Medication optimized and adherence to medications (collected at baseline; 1 mo; 3 mo) • Length of stay (both hospital and ICU) • All-cause rehospitalization (collected in the hospital/postoperatively; 1 mo; 3 mo) • Persistent postsurgical pain (collected at 1 mo; 3 mo) • Patient experience (collected at end of study) • Shared decision making (collected at end of study) 	Research data warehouse	End of Study
---	---	-------------------------	--------------

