In addition to these outcomes, we will also be assessing fidelity of our intervention bundle which will assess the extent to which an intervention bundle is carried out by our perioperative wellness partner, as intended and consistently across different settings, and patients. To track this, we will observe and take notes on the patient and the perioperative wellness partner during the behavioral intervention and medication optimization sessions with the patient and clinician. Observations will involve a member of the research team observing the wellness partner over a period of time or number of intervention sessions. We will capture data on patient interactions with the wellness partner, their delivery of the intervention bundle, any observed barriers and facilitators to the intervention adherence, acceptance and fit within the perioperative workflow. These observation sessions of patients and their wellness

partners will be selected based on a convenience sample. If the patient agrees to audio/video recording, the intervention sessions will be audio recorded (or audio/video if the patient prefers to meet by Zoom teleconference). The observations may be made by a member of the research team reviewing the recorded sessions.

Lastly, we will also obtain various stakeholder perspectives on the intervention bundle after the intervention period has been completed using semi-structured interviews. We will conduct interviews with patients, and caregivers, and the topics of discussions will be guided by an implementation science framework referred to as CFIR (Consolidated Framework of Implementation Research). The interviews will explore the participants' perceptions, attitudes, experiences with the intervention bundle, intervention bundle acceptability and detailed accounts of participants' experiences after the intervention has been stopped with regards to intervention sustainability and maintenance. These insights will inform whether the intervention bundle needs to be changed or adapted before our future trials (see interview guides in Appendix J). Interviews will be conducted via Zoom or telephone and will be digitally recorded and transcribed verbatim.

5 Data Analysis

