The quantitative data will be used to provide baseline and post-intervention comparisons on a number of outcome variables relevant to the intervention, with the hypothesis that performance on these measures will improve post intervention. These data will also be used to estimate effect sizes for further trials so that these are suitably powered. Quantitative data will be tabulated for descriptive purposes. Given the small sample size, a non-parametric approach will be used to calculate effect size data ($r = Z/\sqrt{N}$), where Z is the standardized test-statistic from a Wilcoxon signed-rank test and N is the sample size, along with the associated 95% confidence interval. The r values will be calculated for the timepoint as compared to baseline.

The observation data will be analyzed using open coding and FRAME analytic framework that helps track any adaptations to intervention bundle and delivery. The interview data will be analyzed using thematic analysis [8].

Table 3. Study Calendar

	Time 0	Baseline/ Time 1	In- Hospital / Post-Op	1 mo follow up	2 mo follow up	3 mo follow up	Post- EOS
Patient Consent	X						
Patient Screening (Appendix A)	X						
Patient Baseline surveys (Appendix D)		X					
Caregiver Consent		X					X
Patient Delirium Assessment (Appendix K) pt UB/ 3-D CAM ; & Caregiver if applicable, FAM-CAM		X (pt)	X(pt) twice daily x 3	FAM- CAM if applicable			

1x weekly for 4 weeks.			days post-op	(weekly x 4wks)			
Patient Follow-up 1 & 3 mo Surveys (Appendix G)				X		X	
Patient Monthly Surveys (Appendix L)				X	X	X	
Patient Post-EOS Surveys (Appendix I)							X*
Patient Semi-Structured Interview (Appendix J)							X*
Caregiver Semi-Structured Interview (Appendix J)							X*
Behavioral Activation and Medication Review Intervention Sessions				Approximately 6-12 sessions as needed (per Pt preference) from Baseline, continuing for up to approximately 3 months post-op during study data collection, until EOS.			

*Post-End of Study (EOS) implementation surveys and semi-structured interviews will be completed approximately 2 weeks after EOS assessment.

6 Patient Participant Retention

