The study principal investigator and study coordinator will monitor for breaches of confidentiality and other adverse events on an ongoing basis. Once the PI or study coordinator becomes aware of a reportable adverse event, the event will be reported to HRPO and QASMC according to institutional guidelines. This study does not require QASMC audit or submission of DSM reports.

13 Premature Discontinuation

Subjects will be withdrawn if the investigator decides that discontinuation is in the best interest of the subject, or the subject requests withdrawal from the study. As part of the informed consent process, patients will be notified they may choose to not participate in the study or withdraw at any time with no penalty, and no effect on the standard care they receive.

14 Potential Benefits of the Proposed Research to Participants and Others

Although the study is designed to improve symptoms of depression and anxiety and other outcomes of care, there is no guarantee that the study participants will receive any clinical benefits by participating in the study. This may lead to a clinical intervention that is lifesaving and may not have occurred had the participant not been participating in the study. Given the undertreatment of depression and anxiety in older adults, the minimal risks are acceptable in comparison to the potential benefits in improving the mental health of older adults undergoing surgery.

15 Remuneration

It will not cost the patient anything to participate in the study, and with the flexible design allowing for phone visits, they will not be required to make any extra study visits to the medical center (some visits may be concurrent with a clinic or procedure appointment). Patients will receive remuneration by debit card of \$25 for completion of each data collection study visit at Baseline, 1, 2, 3 month post-op, Post-EOS data collection surveys, and semi-structured interview, up to \$125 after completion of their participation.

16 Funding

The study is funded by the National Institute of Mental Health (NIMH) (P50 MH122351-01A1).

17 References

1. Mangusan, R.F., et al., *Outcomes associated with postoperative delirium after cardiac surgery*. Am J Crit Care, 2015. **24**(2): p. 156-63.
2. Blumenthal, J.A., et al., *Depression as a risk factor for mortality after coronary artery bypass surgery*. Lancet, 2003. **362**(9384): p. 604-9.

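### Acceptability surveys and patient interviews have no exit route, so patients who withdraw or are lost before the end-of-study assessment give neither, and acceptability may be overstated

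*Combined protocol and SAP*

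**What the plan says.** Table 2.1 gives AIM, IAM and FIM one timepoint, Post-EOS; Table 2 gives it as end of study. In the Table 3 calendar, the patient Post-EOS surveys and the patient interview are marked only in the Post-EOS column, and the footnote states that "implementation surveys and semi-structured interviews will be completed approximately 2 weeks after EOS assessment". The text after Table 2.1 agrees: "we will also obtain various stakeholder perspectives on the intervention bundle after the intervention period has been completed using semi-structured interviews". It adds that the interview findings will help decide whether the bundle should be altered before the later trials. Caregiver interviews (Section 3.3.3) come "after the patient's participation in the intervention has been completed".

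On early departure, Section 13 says: "Subjects will be withdrawn if the investigator decides that discontinuation is in the best interest of the subject", or if the patient asks to leave. It describes no exit survey, no exit interview and no recording of the reason. Section 6 provides a letter to hard-to-reach patients, but its purpose is to bring them back to a study session. Section 5 gives no missing-data or denominator rule for these surveys. The data-completeness outcomes listed in Table 2 do not name AIM, IAM or FIM.

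**The concern.** Someone who leaves because the bundle did not suit them holds the information a feasibility study most needs, yet the schedule has no point at which that patient is asked. If such patients rate the bundle lower than those who remain, the reported acceptability is too favourable and some barriers stay hidden.

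This bears on the third objective in the protocol's opening section, which is to find implementation strategies that make the bundle acceptable, feasible and adopted. It also bears on the three trials that the pilot is meant to inform. The primary outcome, reach of the intervention bundle (Section 4.3.1), will show how many did not complete, but not why. As no rule calls for the number surveyed to be set against the number enrolled, a reader of the results might not see how many patients the acceptability figures leave out.

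**Working it through.** The plan states no expected dropout, no acceptability threshold and no sample-size calculation, so it has no figure of its own to reproduce. The check has two parts.

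**1. Who can be measured under the plan as written**

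- Patient completes the bundle and reaches EOS: surveyed and interviewed Post-EOS.
- Patient stops sessions but stays in follow-up: still reachable Post-EOS. The Table 3 footnote sets a time, not an eligibility rule, and Table 3 describes sessions as given as needed and by patient preference. Feedback may come well after the patient stopped, and no split by completion is planned.
- Patient withdraws from the study or is lost before EOS: no AIM, IAM, FIM or patient interview under any section.

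The gap is the third group only.

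**2. How much it could matter (illustration)**

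Input from the documents: N = 45, the maximum number of patients (Section 3). Assumptions: the number unsurveyed, k; a 5-point score (Table 2 gives only a Likert scale with its two end labels); and the gap, g, defined as the mean of those surveyed minus the mean that the unsurveyed would have given. Shares of 10%, 20% and 30% of 45 are taken as 4, 9 and 14 patients.

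Overstatement of the mean = (k / N) × g.

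| k | g = 0 | g = 0.5 | g = 1 |
|---|---|---|---|
| 4 | 0 | 4/45 × 0.5 = 0.04 | 4/45 × 1 = 0.09 |
| 9 | 0 | 9/45 × 0.5 = 0.10 | 9/45 × 1 = 0.20 |
| 14 | 0 | 14/45 × 0.5 = 0.16 | 14/45 × 1 = 0.31 |

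If the unsurveyed would have scored higher, the sign reverses: with g = −0.5 and k = 9, the mean is 0.10 too low.

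For the proportion who find the bundle acceptable, no direction need be assumed. With c favourable responses among N − k respondents, the all-patient figure lies between c / N (all missing unfavourable) and (c + k) / N (all missing favourable). Assume about 80% of respondents are favourable:

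| k | Respondents | c | Observed | Lower bound | Upper bound |
|---|---|---|---|---|---|
| 4 | 41 | 33 | 80.5% | 33/45 = 73% | 37/45 = 82% |
| 9 | 36 | 29 | 80.6% | 29/45 = 64% | 38/45 = 84% |
| 14 | 31 | 25 | 80.6% | 25/45 = 56% | 39/45 = 87% |

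The observed figure is almost the same in each row, while the range consistent with it widens from 9 to 31 percentage points. The plan does not call for that uncertainty to be reported.

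**The case against.** A reader might infer that patients who stop early are not heard at all and that the acceptability sample consists of bundle completers. The documents do not support that. Stopping the bundle is not the same as leaving the study, and nothing limits Post-EOS contact to completers.

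A reader might also infer that the bias is certainly upward. That is plausible but not established. Section 13 includes withdrawals that the investigator decides on, which need not reflect dislike of the bundle, and the documents give neither a dropout rate nor the views of those missed.

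The plan has other sources. Session observations record barriers and acceptance during treatment and may include patients who later leave. Adaptations to behavioral activation are tracked. Non-completion is counted in a primary outcome, so a high acceptability score would be read beside the completion rate. Caregiver interviews are not expressly limited to caregivers of completers. The late timing also has a purpose: the interviews ask about maintenance after the intervention has ended. Finally, implementation potential is exploratory with no decision threshold, and the appendices are not in the text reviewed, so an exit procedure there cannot be ruled out.

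Most of this stands, and it narrows the point. It does not remove it. The observations are a convenience sample of sessions that took place and cannot give a patient's own reason for leaving. Reach counts non-completers without explaining them. The purpose of the late interview is a reason to keep it, not a reason to omit an exit contact. The exploratory label does not change the stated use of the interviews in deciding on changes to the bundle.

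**Conclusion.** The point holds in a limited form. As written, Section 13 and Table 3 leave patients who withdraw or are lost before EOS without any acceptability survey or interview, so acceptability may be overstated. The size cannot be fixed from the documents. Under the stated assumptions (45 patients, about 10% to 30% unsurveyed, a gap of 0 to 1 point on a 5-point score) the overstatement of the mean runs from 0 to about 0.3 points; it is zero if the missing patients hold the same views as the rest. This is a cheap improvement to an exploratory outcome that feeds later design decisions. It does not invalidate the study, and the primary feasibility outcomes are unaffected.

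**What to change.** In Section 13 and Table 3, add an exit contact: patients who stop the intervention or withdraw, and who are willing, are offered the existing AIM, IAM and FIM and a short interview at that time, and the reason for stopping is recorded. Keep the Post-EOS contact for everyone still in follow-up. Where a patient answers at both times, state beforehand which response enters the main summary.

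In Section 5, report the number surveyed out of all enrolled, and show results separately for bundle completers and non-completers. If an appendix already contains an exit procedure, refer to it in Section 13 and Table 3.

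The cost is about one call or REDCap link per stopping patient, with no new instrument. Some patients will decline, so the gap will shrink rather than close. Exit responses are also given at a different time from Post-EOS responses, which is a further reason to show the two groups separately as well as together.

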8.1 List of Protected Health Information collected for study

For Patient and Caregiver Participants, the HIPAA-protected identifiers that will be collected for this study include:

- Name
- Date of birth
- Contact information
- Mailing address
- Phone number
- Electronic mail address
- SSN for the purpose of remuneration

For Patient Participants only, these additional HIPAA-protected identifiers will also be collected for study:

- Dates of services (surgical procedure, hospitalization)
- Medical record number

9 Potential Risks

This study involves minimal risk to subjects. Unlikely but potential risks include errors in medication recommendations or medication withdrawal symptoms, and breach of confidentiality. The risk of medication withdrawal (i.e., from benzodiazepines) is mitigated by slowly tapering rather than stopping these medications. Patients who are identified as being acutely suicidal will be excluded from the study. Nevertheless, since the rate of completed suicide in the USA remains high (i.e., about twice the rate of homicide) and most Americans who commit suicide suffer from depression, all participants eligible to participate in this study are statistically at a relatively higher risk for suicide than the general population. However, the participants' absolute risk for completing suicide during this brief study remains very low (i.e., about 1 in 3,000 to 10,000) and participation in the study does not create or increase the risk of completed suicide; rather, most experts believe that one of the most efficient ways to decrease suicidal risk in older depressed individuals is to treat their depression. Furthermore, all participants will be formally assessed frequently throughout the study. If the study personnel identify that a participant has become acutely suicidal, this participant will be referred to a mental health professional for further evaluation and treatment (see section: Procedures to Minimize Risks). This may lead to a clinical intervention that is lifesaving and may not have occurred had the participant not been participating in the study.

10 Adverse Experiences

Based on the nature of this study, which involves surveys, a cognitive test, and a behavioral intervention, adverse events are exceedingly unlikely. The principal investigator and study coordinator will monitor for breaches of confidentiality and other adverse events on an ongoing basis. If the PI or study coordinator becomes aware of a reportable adverse event, the event will be reported to HRPO according to institutional guidelines.

11 Procedures to Minimize Potential Risks

[name], MD (PI on the Center for Perioperative Mental Health; Co-I on this study) will manage the oversight of the interventions making medication optimization recommendations to reduce the risk of medication error or medication withdrawal symptoms. Algorithms for tapering medications that should not be abruptly discontinued will be employed. We have carried out this deprescribing protocol in several large RCTs and have not seen any problems occur.

Suicide Risk Management: As discussed above, at each assessment point, the research staff will assess for passive death wish, and suicidal ideation, intent or plan when they administer the PHQ-ADS. If a participant endorses suicidal ideation, intent, or plan, the rater will be trained to follow an operationalized protocol (Appendix E) that has been developed to manage high-risk participants in other studies of depressed participants potentially at risk for suicide. This protocol has already been used successfully by [name] team to manage acutely suicidal patients. Briefly, the protocol entails a specific determination of the suicidal risk and prescribes a set of actions. If a participant is determined to be at high and immediate risks, the rater is instructed to stay with the participant until he or she has contacted a study psychiatrist ([name]) to discuss the situation and to devise a plan. In case of extreme emergency, raters are instructed to call their hospital security team or 911 for immediate help and to initiate commitment proceedings.

Patients will be encouraged to check with their physician if there is any question about the safety of any physical activities that are included in the behavioral activation plan. It is possible that the participant may feel uncomfortable completing the surveys or participating in the study sessions. The study sessions and interview can be discontinued at any time, and the patient may refuse to answer any questions that s/he does not wish to answer.

To minimize the risk of breach of confidentiality, we will ensure that protected health information will only be shared with members of the research team. Only data necessary to complete the study will be collected. Data will be coded with UPN wherever possible, and the master list linking names to UPNs will be securely accessible only to the PI, Co-Investigators, data analyst, and primary research coordinator. Electronic data will be stored as detailed in section 8.

12 Data and Safety Monitoring Plan

The specific monitoring plan for this investigation is commensurate with the risks and the size and complexity of the studies planned. Given the nature of the protocol, the risks are likely limited to breach of confidentiality. Data will be monitored and protected as described in Section 8, with PI oversight of data management.

Participation in this study does not entail any physical or medical risks that are greater than those ordinarily encountered in daily life. It is possible that the participant may feel uncomfortable completing the questionnaires. If a participant becomes upset, the PI will talk to the participant either

at that time or will contact the participant by telephone. If any further referrals are deemed necessary (i.e., social work or psychiatry), these referrals will be made in collaboration with the patient's primary medical team.

There is also a risk of breach of confidentiality. All reasonable steps will be taken to ensure that patient privacy is maintained. Hard copy data (i.e. signed informed consent forms) will be maintained in a locked office within a locked suite. Electronic data will be stored on a Washington University password-protected server and never stored on a portable hard drive or laptop computer. Patient data will be identified by a study ID only, with a master key linking patient names with study IDs kept in a separate file accessible only to the Primary Investigator and Research Study Assistant.

The only interventions outside the standard of care for management of the patient's diagnosed condition in this study are the administration of questionnaires, a cognitive test, and medication optimization. We expect that the occurrence of a serious adverse event as it relates to these study interventions to be extremely rare. If a breach of confidentiality were to occur, it would be reported to QASMC and HRPO within 10 days of notification.

The study principal investigator and study coordinator will monitor for breaches of confidentiality and other adverse events on an ongoing basis. Once the PI or study coordinator becomes aware of a reportable adverse event, the event will be reported to HRPO and QASMC according to institutional guidelines. This study does not require QASMC audit or submission of DSM reports.

13 Premature Discontinuation

Subjects will be withdrawn if the investigator decides that discontinuation is in the best interest of the subject, or the subject requests withdrawal from the study. As part of the informed consent process, patients will be notified they may choose to not participate in the study or withdraw at any time with no penalty, and no effect on the standard care they receive.

14 Potential Benefits of the Proposed Research to Participants and Others

Although the study is designed to improve symptoms of depression and anxiety and other outcomes of care, there is no guarantee that the study participants will receive any clinical benefits by participating in the study. This may lead to a clinical intervention that is lifesaving and may not have occurred had the participant not been participating in the study. Given the undertreatment of depression and anxiety in older adults, the minimal risks are acceptable in comparison to the potential benefits in improving the mental health of older adults undergoing surgery.

15 Remuneration

It will not cost the patient anything to participate in the study, and with the flexible design allowing for phone visits, they will not be required to make any extra study visits to the medical center (some visits may be concurrent with a clinic or procedure appointment). Patients will receive remuneration by debit card of \$25 for completion of each data collection study visit at Baseline, 1, 2, 3 month post-op, Post-EOS data collection surveys, and semi-structured interview, up to \$125 after completion of their participation.

16 Funding

The study is funded by the National Institute of Mental Health (NIMH) (P50 MH122351-01A1).

17 References

1. Mangusan, R.F., et al., *Outcomes associated with postoperative delirium after cardiac surgery*. Am J Crit Care, 2015. **24**(2): p. 156-63.
2. Blumenthal, J.A., et al., *Depression as a risk factor for mortality after coronary artery bypass surgery*. Lancet, 2003. **362**(9384): p. 604-9.

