4.3 Evaluation Measures and Outcomes

Preoperative assessments along with preoperative and postoperative surveys (assessments described in 4.1 above) regarding quality of life, depression, and anxiety will be obtained from all study participants. Study participants will be followed for approximately 3 months after their scheduled procedure. They will complete follow-up surveys at approximately 1 month and approximately 3 months after surgery by either web-based survey, mail, or via a telephone interview (or in person if the visit coincides with a clinic visit). Collection of falls data will occur approximately monthly for 3 months by phone with study coordinator, or REDCap, or in person. The results of follow-up surveys will be obtained via secure REDCap e-mail link, mail, or telephone survey. Rehospitalizations will be obtained from patient self-report and/or EHR at the end of study follow-up. Please see Table 2.1 for list of outcomes and details.

Additional pre-operative data related to patient medical, social and surgical history, problems, diagnosis and medication lists will be retrieved from the patient electronic health record using the research data core (RDC). Post-operative data including post-operative acute diagnoses (e.g., complications), additional procedures, postoperative opioid use, pain scores will also be retrieved.

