4.3.2.1 Potential Study Primary Outcomes for Planned RCT

Effectiveness outcomes will include the primary outcome measure of PHQ-ADS, a validated composite scale of depression and anxiety symptoms [7] measured at baseline, 1, and 3 months after surgery. The Behavioral Activation for Depression Scale, or BADS (activation subscale), is our primary measure of target engagement. BADS is a sensitive and pragmatic assessment of the mechanism of change in Behavioral Activation. Approximately three months post-operative is the primary endpoint.

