Participant retention strategies will include flexibility in scheduling follow-up visits and coordination of research (both data collection and intervention) visits with the clinical visits. Remuneration for each data collection study visit will be provided after the final follow-up visit to encourage retention as well. For patients who are difficult to reach by phone, we may utilize a reminder, the *Attempting to Reach You Letter* (Appendix N) to remind them to contact either the Perioperative Wellness Partner or the Study Coordinator for a study session.

7 Protection of Human Subjects

The study will be conducted under appropriate Washington University Institutional Review Board guidance, and use only IRB-approved study procedures and instruments. The study team will follow the protocol under the supervision of the PI, a mentor with several years of experience in the conduct of human volunteer studies, and co-Investigators with extensive expertise in human subject research. All members of the study team are IRB-approved and trained in Good Clinical Practice and Human Subjects Research education.

8 Data Management for Participant Privacy

A unique patient number (UPN) will be assigned at enrollment and used wherever possible on the case report forms (CRF) to identify data, minimizing use of patients' names or personal identifiers in data.

All paper data will be stored under lock and key (two locked doors, e.g., office, file cabinet) and all electronic data will be hosted on a password-protected, firewall-secured server that is only accessible to the research team through password-protected departmental computers. Surveys that are completed electronically will be administered via the Research Electronic Data Capture (REDCap) server. All REDCap email correspondence will be sent using secure survey links. Similarly, interview data from caregivers will follow the same security and storage policies.

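### Section 11 has staff assess suicidality whenever they administer the PHQ-ADS, but Section 4.3 lets both follow-up PHQ-ADS come back by web link or mail, and the body text does not say how the assessment is then made

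*Combined protocol and SAP*

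**What the plan says.** Section 11 sets out suicide risk management. It says of every assessment that "the research staff will assess for passive death wish, and suicidal ideation, intent or plan when they administer the PHQ-ADS". When an answer discloses suicidal thoughts, intent or a plan, a trained rater follows the procedure in Appendix E. Where the risk is judged high and immediate, "the rater is instructed to stay with the participant until he or she has contacted a study psychiatrist".

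Section 4.3.2.1 has the PHQ-ADS "measured at baseline, 1, and 3 months after surgery". Table 2.1 gives the same timepoints and lists the collection mechanism as patient self-report. Section 4.3 says that the 1- and 3-month surveys are completed "by either web-based survey, mail, or via a telephone interview", or in person when a clinic visit coincides. It then repeats the remote routes: "The results of follow-up surveys will be obtained via secure REDCap e-mail link, mail, or telephone survey". The note to Table 2 adds email.

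Section 9 places participants above the general population in suicide risk, while calling the absolute risk very low. It offers as reassurance that "all participants will be formally assessed frequently throughout the study", and says that a participant found to be acutely suicidal will be referred. Section 12 provides that if a participant becomes upset, the principal investigator will talk to the participant "at that time or will contact the participant by telephone".

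**The concern.** Section 11 describes an activity of staff: they enquire into intent and plan while giving the questionnaire. Section 4.3 describes, for the same questionnaire at the same visits, routes on which no staff member need be present. A team could follow Section 4.3 to the letter, receive a completed form by web link or post, and never make the enquiry that Section 11 says is made each time.

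What is at stake is a safeguard that the protocol itself relies on. Section 9 leans on frequent formal assessment when it argues that risk is acceptable in this group. Every enrolled patient has a PHQ-ADS of at least 10. Acutely suicidal patients are excluded, but that exclusion works at entry and not after surgery. For a patient who returns both follow-up forms remotely, the body text provides no Section 11 assessment through the PHQ-ADS after baseline. Section 2 says that the pilot will inform three later trials, so an unreconciled procedure could be carried into them. The feasibility estimates themselves, such as reach, are not affected.

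**Working it through.** There is no planned figure to reproduce. The check compares the passages mode by mode and then sets a ceiling on the number of forms.

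**Which PHQ-ADS are exposed.** The baseline value is the one collected at screening (Section 4.1), and Section 3.3.2 has a trained team member collect it by phone or in person. Staff contact is therefore built in. That leaves the 1-month and 3-month forms.

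**Modes allowed at 1 and 3 months.**

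| Mode | Allowed by | Staff contact built in? | Section 11 assessment delivered as written? |
|---|---|---|---|
| Telephone | Section 4.3, Table 2 note | Yes | Yes |
| In person | Section 4.3 | Yes | Yes |
| Web or e-mail link | Section 4.3, Table 2 note | No | Not stated |
| Mail | Section 4.3 | No | Not stated |

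**Does the word for giving the survey settle it?** No. Section 8 uses the same verb for unattended completion: "Surveys that are completed electronically will be administered via the Research Electronic Data Capture (REDCap) server". The point rests on what staff are said to do. An enquiry by staff into intent and plan needs contact, and a returned form does not supply it.

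**Does other text assign the assessment elsewhere?**
- Section 4.2.1 and Table 3: about 6 to 12 sessions, roughly every one or two weeks, with social workers or therapists. Their number and timing depend on patient preference. The assessment is not assigned to them.
- Section 9: referral if personnel identify acute suicidality. It does not say how a remote return would lead to that identification.
- Section 12: investigator contact if a participant becomes upset. This concerns distress and does not mention review of a returned form.

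**Ceiling on the number of forms.** Inputs: up to 45 patients (Section 3) and two follow-up PHQ-ADS each (Section 4.3.2.1).
- Follow-up forms: 45 × 2 = 90 at most.
- All scheduled PHQ-ADS: 45 × 3 = 135 at most, so the follow-up forms are 90/135 = 67% of them.
- Forms returned without staff contact = share by web, mail or email × 90. The documents give no share, so the range is 0 × 90 = 0 to 1 × 90 = 90.

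**The case against.** The strongest reply is that this is an omission and not a contradiction. Section 4.3 only permits modes, Section 11 imposes a duty, and a team could satisfy both by adding staff contact around a remote return. Section 11 is also openly a summary of Appendix E, so less detail is to be expected there. That is fair as to what a careful team might do. But nothing in the body text requires the added contact, and a stated safeguard that can lapse while a permitted route is followed is more than missing detail.

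Three further replies carry weight. First, Section 11 does have a trigger, endorsement by the participant, and this could occur on a self-completed form. What is missing is who reads the form, when, and how the assessment follows. Second, the instruction that the rater stay with the participant is weak evidence. It applies only once risk is judged high and immediate, and read physically it would trouble telephone completion too. The point does not depend on it. Third, mitigation is substantial: regular sessions with mental health staff, a psychiatrist on the medication team (Section 4.2.2), and a referral duty that applies whatever the survey mode. These reduce the chance that a patient at risk goes unnoticed, but they do not deliver the Section 11 assessment.

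Telephone may also be the usual mode. Section 4.1 has falls data collected by phone alongside other assessments, Section 6 speaks of reaching patients by phone, and Section 15 refers to phone visits. The number of remote returns could therefore be small or nil.

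**Conclusion.** The point holds for the body text. For follow-up PHQ-ADS returned by web link, mail or email, the assessment stated in Section 11 is not delivered as written, and no other section takes it over. The exposure is at most 90 forms, with the actual number unknown and possibly zero. Telephone, in-person and screening completions are unaffected. It should be fixed, because it concerns a safeguard on which the risk section relies and the repair is specific and cheap.

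A reader might infer more than the documents support:
- That the study has no procedure for suicidality in remote returns. Appendices E and G are cited but were not available for review, and either may cover them. For the same reason, no higher severity can be argued from what Appendix E might lack.
- That patients go unobserved after surgery. The sessions and the referral duty say otherwise.
- That a minimum number of forms is affected. Both the cohort size and the total in Section 3 are stated as upper limits, so only the ceiling of 90 is supported.

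**What to change.** Reconcile Sections 4.3 and 11 so that the assessment stated in Section 11 is delivered for every mode permitted for the follow-up PHQ-ADS. The Table 2 note should agree with the result. How this is done is for the sponsor's clinicians, and this review proposes no clinical rule. If Appendix E already covers web and mail returns, a sentence in each of the two sections saying so is enough.

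The cost is protocol wording and some time from existing staff for each web or mail return. The documents give no basis for a figure in hours. If the sponsor chose to restrict modes, PHQ-ADS completeness, the secondary feasibility outcome, could fall slightly, and that should be weighed when the manner is chosen.
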